Based on the biological data outlined above, the PTC299 exposure after dosing at 1.2 mg/kg BID would result in significant reduction of DHODH enzyme activity in the clinic.

No serious adverse events were reported in Study 002.

Table 2: Summary of PTC299 Pharmacokinetics in Healthy Volunteers when Administered with the Capsule Formulation (~2.5x of the Bioavailability of the Tablet Formulation) (Study PTC299-ONC-002-HV)

Approximate	Dose	Day	PTC299						
Tablet (mg)	Capsule (mg/kg)	Frequency							
				T _{max} (h)	T _{1/2} (h)	C _{max} (µg/mL)	AUC₀₊₄ (μg∗hr/mL)		
50	0.3	BID	1	4.0	NA	0.28	4.31		
125	0.6	1		3.0		0.71	10.1		
200	1.2	1		3.5	7	1.14	18.0		
280	1.6	TID		3.0		1.67	37.1		
50	0.3	BID	7	3.5	164	0.51	8.44		
125	0.6]		4.0	210	1.11	18.6		
200	1.2			4.0	228	2.11	32.9		
280	1.6	TID		3.0	225	3.53	78.6		

Abbreviations: AUC₀₋₄, area under the concentration curve from hour 0 to 4; C_{max} , maximal concentration; $T_{1/2}$, half-life; T_{max} , time to maximal concentration

Proposed dosing regimen

Subjects will be dosed for a total of 14 days and followed for an additional 14 days without dosing. Subjects will receive oral tablets containing PTC299 or matched placebo 200 mg BID (morning and evening) on Days 1 to 7 and 50 mg QD on Days 8 to 14. Subjects will subsequently be followed from Day 15 to 28, and there will be a telephone call at Day 60 to assess AEs, SAEs, and deaths.

The dosing regimen takes into consideration the typical progression of the disease including the disease characteristics in patients who are hospitalized with COVID-19. The dosing of 200 mg BID for the first 7 days will raise the exposure of the drug quickly to accommodate the need for rapid onset of PTC299 activity. The dosing of 50 mg QD for the second 7 days will prevent the exposure from substantially decreasing. Importantly, clinical evidence indicates that this dosing regimen should be well tolerated.

The dosing regimen is based on extensive clinical, safety, and clinical pharmacology experience with the capsule formulation of PTC299, which was used in the prior solid tumor clinical studies. The results from clinical study PTC299-ONC-002-HV (Study 002) indicate that 200 mg BID dosing would raise the exposure of PTC299 within 7 days to the anticipated therapeutic range (23 to 33 μ g*hr/mL).

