4.2. Inclusion Criteria

Before enrollment in the study, subjects must fulfil all of the following criteria:

- 1. Subject (or legally authorized representative) is willing and able to provide informed consent and comply with all protocol requirements.
- Agrees to the collection of nasopharyngeal swabs and venous blood and all other protocol-specified procedures.
- 3. Male or non-pregnant female adult ≥18 years of age at time of enrollment.
- 4. Hospitalized and has laboratory-confirmed infection with SARS-CoV-2.
- 5. Symptom onset was ≤14 days prior to Screening
- 6. Has SpO₂ <94% on room air
- 7. Has at least one of respiratory rate >24 breaths/minute or cough
- 8. Lung involvement as confirmed by radiographic infiltrates observed on imaging (chest X-ray, CT scan, or an equivalent test)

- 9. Women of childbearing potential (as defined in (CTFG 2014)) must have a negative pregnancy test at screening and agree to abstinence or the use at least one of the following highly effective forms of contraception (with a failure rate of <1% per year when used consistently and correctly). Contraception or abstinence must be continued for the duration of the study following discharge from the hospital, and for up to 50 days after the last dose of study drug:
 - combined (estrogen and progestogen containing) hormonal contraception associated with inhibition of ovulation:
 - oral
 - intravaginal
 - transdermal
 - progestogen-only hormonal contraception associated with inhibition of ovulation:
 - oral
 - injectable
 - implantable
 - intrauterine device
 - intrauterine hormone-releasing system
 - vasectomized partner with confirmed azoospermia

All females will be considered of childbearing potential unless they are postmenopausal (at least 12 months consecutive amenorrhea in the appropriate age group without other known or suspected cause) or have been sterilized surgically (eg, bilateral tubal ligation, hysterectomy, bilateral oophorectomy).

10. Men sexually active with women of childbearing potential who have not had a vasectomy must agree to use a barrier method of birth control during the study following discharge from the hospital and for up to 50 days after the last dose of study drug.

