Urinalysis	X	Х	X	Х	X	Χ				
Concomitant medications	Х	Х	Х	Х	Х	Χ	Х	Χ		
Study drug administration		X	Х	Х	Х	Х				Study drug will be administered orally at 200 mg BID on Days 1 to 7 followed by 50 mg QD on Days 8 to 14. Should a subject be discharged prior to Day 14, tablets will be dispensed to take at home and compliance will be recorded at Day 14.
Blood draw for PK		X		X		X				On Days 1 and 7, blood samples for PK assessment will be collected pre-dose (0) and at 6 hours post-dose and on Day 14 at pre-dose (0) and 4 hours post-dose (morning dose only). An ad hoc PK assessment will be performed in the case of hepatotoxicity (see also Section 7.3).
Blood draw for cytokine assessment		X	X	X		X		Х		
Blood draw for acute phase protein assessment		Х	Х	Х		Х		Х		
Antibody titer assessment		Х						Х		

Assessment/Activity	Screening	Day	Treatment Period				Follow-up)	Notes	
_		1	Days	Day	Days	Day 14/	Days	Day 28/	Day	Screening and Day 1 should occur within a
			2-6	7	8-13	EOT	15-27	EOS	60 ±3	1-day period; where they occur on the same day, assessments need not be repeated. Subjects remaining in hospital will undergo the assessments specified. All subjects will undergo the assessments specified for Day 14, Day 28, and Day 60 even if they are discharged from the hospital prior to Day 28.
Adverse events	X	X	X	X	X	X	X	X	X	At Day 60, the visit will be a telephone call to record AEs, SAEs, and deaths for all subjects except those who die or are lost to follow-up or withdraw consent.

Abbreviations: βHCG, beta human chorionic gonadotropin; BID, twice daily; EOS, end of study; EOT, end of treatment; PK, pharmacokinetic; QD, once daily, WHO, World Health Organization; WOCBP, women of childbearing potential.

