7.5.2. Definition of Serious Adverse Events

An SAE is an untoward medical occurrence or effect associated with the use of a study drug at any dose, regardless of whether it is considered to be related to the study drug, which results in one of the following:

- Death. This includes all deaths on treatment or within 30 days after last study drug administration, including deaths due to disease progression. Any death occurring later than 30 days following the last dose need not be reported as an SAE unless it is a result of an event that started within the period covered by the on-study definition. The reported AE should be the event that caused the death. In addition, any AE resulting in death that occurs subsequently to the AE reporting period and that the investigator assesses as possibly related to the study drug should also be reported as serious.
- A life-threatening condition. This refers to an event in which the subject was at risk of
 death at the time of the event. It does not include an event that, had it occurred in a
 more severe form, hypothetically might have caused death.
- Hospitalization or prolongation of existing hospitalization (excluding hospitalizations for administration of the study drug, procedures required by the study protocol, or treatment-related diagnostic procedures; other planned hospitalizations; or hospitalizations related only to progression of disease). Progression of disease resulting in transfer to ICU, mechanical ventilation, or other medically important event (at the discretion of the investigator) would be considered SAEs. Treatments in the emergency room for procedures such as hydration that do not require admitting the subject to the hospital and observational durations in the emergency room for less than 24 hours do not fall into this category.
- Persistent or significant disability or incapacity or substantial disruption of the ability to conduct normal life functions.

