- Any other medically important event that the investigator or the sponsor judges to be serious or which is defined as serious by the regulatory agency in the local country. These are AEs that might not be immediately life-threatening or result in death or hospitalization but might jeopardize the subject or might require intervention to prevent one of the other outcomes listed above. Medical judgment should be exercised in deciding whether an AE is serious based on above definition. Examples of such events are intensive treatment in an emergency room or at home for allergic bronchospasm, blood dyscrasias or convulsions that do not result in hospitalization, or development of drug dependency or drug abuse.
- A pregnancy resulting in spontaneous abortion, stillbirth, neonatal death, or congenital anomaly (including that in an aborted fetus).

Note that any SAEs occurring at any time up to Day 60 should be reported to the sponsor if the investigator becomes aware of them.

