8.4.4.4. Adverse Events

Summary information (the number and percent of subjects by treatment) will be tabulated for:

- Treatment-emergent adverse events (TEAEs)
- Treatment-related AEs
- TEAEs by severity
- SAEs
- AEs leading to discontinuation
- AESIs

Summaries will be presented by treatment group and categorized by MedDRA System Organ Class and Preferred Term. The frequencies of AEs displayed will be the crude rates that represent the number of subjects experiencing AEs divided by the total number of subjects.

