#### **4.10.1. Adverse Events**

All adverse events (AEs) will be coded using the MedDRA. The MedDRA version will be indicated in the footnote of relevant AE tables based on the current version used in the clinical data.

AEs will be analyzed in terms of treatment-emergent adverse events (TEAEs), which are defined as any AEs that occurring on or after the first study treatment through 30 days after the last dose, or any AEs occurring before the first study treatment but worsening during the treatment through 30 days after the last dose.

A treatment related TEAE is defined as TEAE that is suspected (possibly or probably related) by the investigator to be related to the study treatment. The severity/intensity of AEs will be graded 1 to 5 according to the National Cancer Institute (NCI) Common Terminology Criteria for Adverse Events (CTCAE) version 5.0. For AEs not described in CTCAE criteria, the intensity will be assessed by the investigator as mild (Grade 1), moderate (Grade 2), severe (Grade 3), life threatening (Grade 4), and fatal (Grade 5).

An overview of TEAE summary by treatment groups table will be provided with following information:

- The number of subjects with at least one TEAE
- The number of subjects with at least one treatment related TEAE
- The number of subjects with at least one Grade 3 or Grade 4 TEAE
- The number of subjects with a Grade 5 TEAE (Fatal)
- The number of subjects with at least one SAE

The number of subjects with at least one TEAE leading to treatment discontinuation.

All TEAEs will be summarized by MedDRA system organ class (SOC), and PT. If a subject experiences multiple AEs under the same SOC, the subject will be only counted once for the SOC with the greatest severity. Similarly, if a subject experiences multiple AEs under the same PT and SOC, the subject will be counted only once for the PT with the greatest severity.

The table will be sorted by the descending order of the frequency of SOC then by the descending order of the frequency of PT under SOC based on the PTC299 column.

In addition, the following summary tables will be provided:

- All TEAE by descending frequency of PT
- All TEAE by maximum severity under each SOC and PT
- SAE by SOC and PT
- Treatment related TEAE by SOC and PT
- TEAE leading to treatment discontinuation by SOC and PT

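### The TEAE window closes 30 days after the last dose while AEs are collected to Day 60, so later AEs, including those judged related, get no between-arm table

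*SAP*

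**What the plan says.** SAP 4.10.1 puts the AE analysis on a treatment-emergent basis. An event counts if it is one of "any AEs that occurring on or after the first study treatment through 30 days after the last dose", or if it began before dosing and worsened within the same limit. A treatment-related event is then defined as a TEAE that the investigator judges possibly or probably related. Non-treatment-emergent AEs are given in by-subject listings.

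Collection runs longer. Protocol Table 3 (Section 7.1) states: "At Day 60, the visit will be a telephone call to record AEs, SAEs, and deaths for all subjects", apart from those who have died, been lost or withdrawn consent. The call has a window of ±3 days. Planned dosing ends on Day 14 (Protocol 3.2: "Subjects will be dosed for a total of 14 days and followed for an additional 14 days without dosing").

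Three other parts of the Protocol bear on the choice of window:
- **Half-life.** In Table 2 (Section 3.2), the Day 7 row for the capsule dose matched to the 200 mg tablet reads "4.0 228 2.11 32.9" (Tmax, half-life in hours, Cmax, AUC).
- **Contraception.** Section 4.2 requires it "for up to 50 days after the last dose of study drug".
- **Late deaths and SAEs.** Section 7.5.2 says "Any death occurring later than 30 days following the last dose need not be reported as an SAE", with an exception for deaths that result from an event begun earlier. It also says "any SAEs occurring at any time up to Day 60 should be reported to the sponsor" if the investigator learns of them.

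Protocol 8.4.4.4 lists treatment-related AEs as a separate item from TEAEs and specifies "crude rates that represent the number of subjects experiencing AEs divided by the total number of subjects". The Protocol does not define the TEAE window. SAP Section 5 declares no change from the Protocol's planned analyses.

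**The concern.** The window that decides which AEs are compared between arms is shorter than the period over which AEs are collected. It is also shorter than five half-lives of a slowly eliminated drug. The part cut off is what the Day 60 call adds.

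The related-event definition makes this matter more. The secondary safety objective is assessed by drug-related AEs, and Protocol 7.5.6 asks sites to record possibly related events even after the reporting period. Yet an AE with onset on Day 50 that the investigator judges possibly related cannot enter the SAP's treatment-related table, because it is not a TEAE. The Protocol's own list puts no such limit on treatment-related AEs.

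The window also runs from each subject's own last dose, so its calendar length depends on when dosing stopped. Rates are crude proportions, so nothing adjusts for that difference. If stopping patterns differ between arms, so does the counted time.

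**Working it through.** The plan states no figure that this point must reproduce. The check is direct arithmetic on four inputs:
- window end = last-dose day + 30 (SAP 4.10.1)
- collection to Day 60, ±3 (Protocol Table 3)
- planned last dose on Day 14 (Protocol 3.2)
- terminal half-life of 164 to 228 h on Day 7, with 228 h at the 200 mg-equivalent dose (Protocol Table 2)

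**Step 1: calendar coverage.** Days outside the window = 60 − (last-dose day + 30).

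| Last dose | Window ends | Days outside, to Day 60 |
|---|---|---|
| Day 14 | Day 44 | 16 (13 to 19 with the ±3-day call) |
| Day 7 | Day 37 | 23 |
| Day 3 | Day 33 | 27 |
| Day 1 | Day 31 | 29 |

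An onset on Days 32 to 44 (13 days) is counted for a completer but not for a subject who stopped on Day 1.

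**Step 2: window length in half-lives.** Half-lives = hours ÷ t½. Fraction remaining = 0.5^(half-lives), assuming a single-exponential decline.
- 228 h = 9.5 days. 30 days: 720 ÷ 228 = 3.16 half-lives, 11.2% remaining.
- 164 h: 720 ÷ 164 = 4.39 half-lives, 4.8% remaining.
- Five half-lives at 228 h: 5 × 9.5 = 47.5 days.
- Day 60 call for a completer: 60 − 14 = 46 days; 1104 ÷ 228 = 4.84 half-lives, 3.5% remaining.
- 50-day contraception period: 1200 ÷ 228 = 5.26 half-lives, 2.6% remaining.

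At the longest half-life, the Day 60 contact is close to five half-lives after a completer's last dose. The 30-day limit is not.

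**Step 3: is 11.2% realistic?** In Table 2 the AUC at this dose rises from 18.0 on Day 1 to 32.9 on Day 7, a ratio of 32.9 ÷ 18.0 = 1.83. The AUC is read here as 24-hour exposure: the printed 0–4 hour label cannot fit, since 4 h × Cmax 1.14 = 4.56. Superposing 14 doses every 12 h in a one-compartment model with a 228 h half-life predicts a ratio of 7.3. The same model gives 1.60 at 12 h and 1.90 at 16 h, so 1.83 corresponds to an effective half-life of about 15 to 16 h. The slow terminal phase therefore seems to carry a small share of exposure, and 11.2% is an upper figure for carry-over. The half-lives also come from healthy volunteers on the capsule, not from patients on the tablet.

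**Step 4: does stopping early change the carry-over?** No. The window runs from the last dose, so the fraction left when it closes is the same for every stop day. A subject who stops during the first week has also accumulated less drug than one who completes that week.

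**Step 5: what happens to events after the window?**
- AEs that are not serious and not AESIs: listed by subject, with no by-arm table.
- Treatment-related AEs: excluded from the treatment-related table, because that table is limited to TEAEs.
- SAEs: the SOC/PT table carries no TEAE label, but the SAE row in the overview sits inside a TEAE summary, so its window is unclear.
- AESIs (SAP 4.10.3): summarised by arm, with no TEAE limit stated.
- Deaths (SAP 4.10.2): tabulated by arm at Day 28 and Day 60.

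**The case against.** The case for leaving the plan alone has force on several points.

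- **Late events are not lost.** A reader might infer that they are discarded. The documents do not support that. Non-TEAEs are listed, Day 60 deaths are tabulated by arm, and the SAE and AESI summaries state no TEAE limit. A fatal AE that began inside the window still counts as a TEAE even if death comes later. This stands, and it narrows the point to AEs without a by-arm table of their own. A listing does not give a comparison between arms.
- **Coverage of the intensive period is complete.** Under Protocol 6.2, subjects are assessed to Day 28 unless they die, are lost or withdraw consent, and even a Day 1 stop has a window to Day 31. After Day 28 the only scheduled contact is the telephone call, with no scheduled safety laboratory tests. Days outside the window should not be weighed like inpatient days. This stands too.
- **The bias has no known direction.** A reader might infer that crude TEAE rates favour PTC299, because the hepatic, lymphocyte and hemoglobin rules could stop more subjects on active drug. The documents give no stopping rates. Those rules begin with a temporary stop and retest, and disease progression also ends treatment, which could affect placebo. Only the unequal window length is established.
- **Carry-over is not worse in early stoppers.** Steps 3 and 4 above settle this.
- **The 50-day period is not an AE attribution rule.** It governs contraception and pregnancy reporting. It shows only that the Protocol uses a longer post-dose horizon for another purpose.
- **The SAP contradicts no Protocol window.** That is true, since none is defined, and 30 days matches the Protocol's cutoff for reporting deaths as SAEs. It does not explain the narrowing from treatment-related AEs to treatment-related TEAEs.

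**Conclusion.** The concern holds in a limited form. The 30-day window leaves 16 days of planned AE collection outside the between-arm TEAE tables for a completer, and up to 29 for an early stopper. It equals 3.2 half-lives at 228 h. Because related events are defined as a subset of TEAEs, late AEs judged related are also left out of the table that most directly addresses the safety objective.

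The calendar figures rest only on the stated definitions and a call at Day 60. The half-life figures assume single-exponential decline at the healthy-volunteer terminal half-life, and about 11% residual drug should be read as an upper figure. The documents give no AE rate after Day 30, so neither the number of events affected nor the direction of any bias can be computed. This is an inexpensive improvement to the safety tables, not a flaw that undermines the safety analysis.

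Separately, the two statements in Protocol 7.5.2 on late deaths and late SAEs pull in different directions, even with their qualifying clauses.

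**What to change.** In SAP 4.10.1, add by-arm tables of all AEs and of treatment-related AEs from first dose through the Day 60 contact, for every treated subject and with the same window in both arms. Equivalently, extend the TEAE window to that contact and keep the 30-day version as supportive.

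State in SAP 4.10.1 and 4.10.3 that the SAE and AESI tables run to Day 60. If the treatment-related table stays limited to TEAEs, record that in SAP Section 5 as a departure from Protocol 8.4.4.4.

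Reconcile the two statements in Protocol 7.5.2, on deaths later than 30 days after the last dose and on SAEs up to Day 60, with each other and with the Day 60 call.

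The cost is SAP wording and one extra table set. No new data are needed. The drawback is that some unrelated late background events will enter the counts in both arms.

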#### **4.10.2. Death**

The number and the percentage of deaths at Day 28 and Day 60, respectively, will be summarized by treatment groups.

All deaths will be presented in a by-subject listing.

#### **4.10.3. Adverse Events of Special Interest (AESI)**

Adverse events that may be indicative of hepatotoxicity (including the lower level MedDRA term of hepatotoxicity or drug-induced hepatotoxicity) are considered adverse events of special interest (AESIs). These include:

- ALT increase Grade  $\geq 3$  ( $>5 \times \text{ULN}$ )
- AST increase Grade  $\geq 3$  ( $>5 \times \text{ULN}$ )
- Tbili increase  $>2 \times \text{ULN}$
- ALP  $\geq 2 \times \text{ULN}$

The number and the percentage of subjects experiencing AESIs will be summarized by each criterion and overall, and by treatment groups.

#### 4.10.4. Clinical Laboratory Evaluations

Laboratory values will be presented in standard units. If any assessment is performed at both local and central laboratories, the value from central laboratory will be used in the analysis. In the event of repeated values for a test at a visit from same laboratory, the last non-missing value at that visit will be used

Descriptive statistics will be provided for each clinical laboratory parameter at baseline, at each study visit post baseline for actual values and changes from baseline by treatment groups. Unless otherwise specified, only scheduled visits will be included in the summary tables.

Clinical laboratory values will be graded according to NCI CTCAE version 5.0 for applicable tests. A summary table of the worst CTC grade post baseline during the treatment period of laboratory data will be provided by treatment groups. For the worst CTC grade tables, unscheduled laboratory values will be considered as well.

A by-subject listing will also be provided for laboratory data. Laboratory values that are outside the normal range will also be flagged in the data listings. Any out-of-range values that are identified by the investigator as being clinically significant will also be shown in a listing.

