6.1.1. Discontinuation due to Abnormal Liver Function

Several specific measures will be undertaken to identify the risk of hepatotoxicity in subjects and manage high drug exposure. To avoid hepatotoxicity, PTC has implemented a comprehensive monitoring of liver function tests (LFTs), including ALT, AST, total bilirubin (Tbili), and alkaline phosphatase (ALP). During hospitalization, the LFTs will be monitored daily during treatment and at Day 28. An HAC will comprehensively monitor all hepatic abnormalities and continually evaluate hepatic safety during the study.

Consistent with the Food and Drug Administration Drug Induced Liver Injury (DILI) guidance (FDA 2009), subjects will be closely monitored for any of the following:

- Any serum ALT or AST Grade ≥ 3 ($>5 \times ULN$), regardless of baseline
- Tbili (>2×ULN), whether or not serum ALT or AST values are elevated; if such an elevation occurs, direct bilirubin will be measured

If any of the above conditions are met, the following steps will be taken:

- Temporarily stop dosing study drug and retest ALT, AST, and Tbili within 72 hours to confirm changes. Subjects with Grade 3 liver function abnormalities will be monitored until these values return to the baseline.
- Notify the sponsor and medical monitor (see also Section 7.5.3 and Section 7.5.10)
- Resume dosing with study drug if the retesting does not confirm the magnitude of the abnormality(ies), after discussion with the medical monitor.
- Evaluate ALT, AST, Tbili, and ALP daily, until stable or resolved.
- Consider further work-up in consultation with the medical monitor.

Permanent discontinuation of study drug for abnormal liver function should be considered by the investigator when a subject meets one of the conditions outlined above or if the investigator believes that it is in best interest of the subject. After each abnormal liver function event that meets the criteria for discontinuation, the HAC will meet to assess the severity and causality of the event and generate a case report.

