**Table 2: Schedule of Events and Study Parameters**

Assessment/Activity	Screening	Day 1	Treatment Period				Follow-up			Notes
			Days 2-6	Day 7	Days 8-13	Day 14/EOT	Days 15-27	Day 28/EOS	Day 60 ±3	
Informed consent	X									
Screening and Day 1 should occur within a 1-day period; where they occur on the same day, assessments need not be repeated. Subjects remaining in hospital will undergo the assessments specified. All subjects will undergo the assessments specified for Day 14, Day 28, and Day 60 even if they are discharged from the hospital prior to Day 28.
 
(WHO 2020)
 
WOCBP only. Pregnancy test can be serum βHCG or urine. The Day 60 test should be taken at home and self-reported during telephone contact.
 
Vital signs will include oxygen saturation daily for primary endpoint assessment in addition, temperature, respiratory rate, and blood pressure will also be assessed.
 
Cough and dyspnea are assessed daily on a patient reported scale of severe, moderate, mild, or absent.
 
Full physical examination (including a minimum of general appearance, head, eyes, ears, nose, mouth, throat, heart, thyroid, chest and lungs, abdomen, extremities, neuromuscular system, skin, and lymph nodes) will be completed during screening; at all other timepoints the examination will be targeted.
 
X-ray taken within 24 hours prior to Screening will be accepted. CT scan will be accepted in place of the X-ray if taken with 48 hours prior to Screening.
 
Nasopharyngeal swab will be taken on Days 1, 2, 4, 7, 14, and 28.
 
Assessments taken within 24 hours prior to Screening will be accepted.

Medical history	X									
WHO ordinal scale assessment	X									
Pregnancy test	X						X	X		
Vital signs	X	X	X	X	X	X	X	X		
Cough and dyspnea assessments	X	X	X	X	X	X	X	X		
Body weight and height	X									
Physical examination	X	X	X	X	X	X		X		
Chest X-ray	X					X				
Nasopharyngeal swab		X	X	X		X		X		
Hematology, coagulation, and clinical chemistry assessment	X	X	X	X	X	X		X		

PTC299-VIR-015-COV19  
Statistical Analysis Plan

Assessment/Activity	Screening	Day 1	Treatment Period				Follow-up			Notes
			Days 2-6	Day 7	Days 8-13	Day 14/EOT	Days 15-27	Day 28/EOS	Day 60 ±3	

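### The worst-grade laboratory table in SAP 4.10.4 covers only the treatment period, so it omits Day 28 and every value after Day 14, and its end is undefined for subjects who stop early

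*SAP*

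**What the plan says.** SAP 4.10.4 (Clinical Laboratory Evaluations) sets the window: "A summary table of the worst CTC grade post baseline during the treatment period of laboratory data", shown by treatment group. It adds: "For the worst CTC grade tables, unscheduled laboratory values will be considered as well". The second sentence widens the type of value used, but not the period.

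The SAP gives no definition of treatment period. The only layout is in the schedule of events (Protocol Table 3, SAP Table 2), where the Treatment Period columns end at Day 14/EOT and Days 15-27, Day 28/EOS and Day 60 stand under Follow-up. Protocol 3.2 agrees: "Subjects will be dosed for a total of 14 days and followed for an additional 14 days without dosing", and "Subjects will subsequently be followed from Day 15 to 28".

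The schedule row "Hematology, coagulation, and clinical chemistry assessment" is marked at screening, on each treatment-period column, and again at Day 28. It is not marked for Days 15-27. The Day 28 assessments apply to all subjects, including those already discharged.

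For adverse events the window is longer. SAP 4.10.1 counts events as treatment-emergent "through 30 days after the last dose".

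**The concern.** Two safety summaries of the same subjects use different windows. A Grade 3 laboratory value on Day 28 can be a treatment-emergent adverse event and yet be missing from the laboratory grade table. Under Protocol 7.5.1, an abnormality that needs no intervention or further investigation is not reported as an adverse event at all, so after Day 14 it is counted by severity in neither place.

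The drug is eliminated slowly, so the first two weeks off dosing are still a time of exposure. The protocol itself schedules a safety sample at the end of them.

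The window is also unclear for subjects who stop early. For a liver trigger, Protocol 6.1.1 says: "Temporarily stop dosing study drug and retest ALT, AST, and Tbili within 72 hours to confirm changes". It then asks for daily liver tests until they settle. Protocol 6.1.2 has a similar hold and 72-hour retest for low haemoglobin or lymphocytes. Whether values after a permanent stop count as within the treatment period is left to the programmer, and two programmers could produce different tables.

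**Working it through.** The plan states no figure for this point, so there is none to reproduce. The check compares windows and then sizes the gap.

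**1. What falls outside the table.** With the period ending on Day 14 and follow-up to Day 28, 28 − 14 = 14 days (Days 15-28) are excluded for every subject. They contain one scheduled laboratory sample (Day 28) plus any unscheduled values.

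**2. Early stoppers.** Two readings are possible. The calendar reading takes the schedule's block, to Day 14. The last-dose reading takes first to last dose, as SAP 4.8.1 does for treatment duration. For a permanent stop on day s, the days excluded through Day 28 are 14 on the calendar reading and 28 − s on the last-dose reading. The post-stop days kept only by the calendar reading are 14 − s.

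| Last dose on | Excluded, calendar | Excluded, last dose | Post-stop days kept only by calendar |
|---|---|---|---|
| Day 5 | 14 | 23 | 9 |
| Day 10 | 14 | 18 | 4 |
| Day 14 | 14 | 14 | 0 |

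Day 28 is excluded on both readings. Values during a temporary hold followed by resumed dosing are included on both.

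**3. The adverse event window.** For a last dose on Day 14 it runs to Day 14 + 30 = Day 44. Even for a single dose on Day 1 it runs to Day 31. It therefore contains the Day 28 sample for every treated subject.

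**4. Drug remaining at Day 28.** Protocol Table 2 gives Day 7 half-lives from 164 h (lowest dose row) to 228 h (the row matched to the 200 mg tablet twice daily). The time from Day 14 to Day 28 is 14 × 24 = 336 h. With simple one-compartment decay, the fraction of the Day 14 level left is 0.5^(336 / half-life):
- 164 h: 0.5^(336/164) = 0.24
- 228 h: 0.5^(336/228) = 0.36

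**5. Where values after Day 14 can still appear.**
- By-visit summaries (SAP 4.10.4): Day 28, as descriptive statistics. Scheduled visits only, with no grade counts.
- Liver categories and potential Hy's law cases (SAP 4.10.4.1, Table 1): ALT, AST and bilirubin only, with no window stated.
- AESI counts (SAP 4.10.3): liver criteria only, with no window stated.
- Listings: all values, with out-of-range flags.

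An unscheduled haemoglobin or lymphocyte value after Day 14 thus appears only in a listing, unless it was also reported as an adverse event. A Day 28 value of either test appears in a by-visit summary but is never counted by worst grade.

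**The case against.** The strongest reply is that this is one descriptive table among several and that an on-treatment worst-grade table is a normal choice. Hepatotoxicity, the event of special interest, is well covered elsewhere. The AESI counts and Table 1 carry no end-of-treatment cut, AESIs are reported within 24 hours, and the hepatic committee writes a case report on each liver event that meets the discontinuation criteria. Day 28 values are summarised by visit, with minimum and maximum. Laboratory abnormalities that need action can be treatment-emergent adverse events. All of this stands, and it confines the gap to graded summaries, mainly of non-liver tests.

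A reader might go further and infer that any liver or blood value peaking after a toxicity stop is lost, and that this favours the arm with more stopping. The documents do not support that as a general statement. It needs the last-dose reading and a permanent stop. On the calendar reading, which is the only one the documents lay out, the cut-off is the same day in both arms and values from the stop to Day 14 are kept. The stops in Protocol 6.1.1 and 6.1.2 are temporary at first. The required daily retesting applies to liver tests, while the blood-count rule asks only for a retest within 72 hours.

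It is also fair to say that the residual drug fraction is not a count of missed grades. It is a share of the Day 14 level, which follows a week on the lower dose.

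**Conclusion.** The point holds in a limited form. On either reading of treatment period, the worst-grade table omits the scheduled Day 28 sample and all unscheduled values after Day 14. That is 14 days per subject who completes dosing, all inside the adverse event window. About 24% to 36% of the end-of-treatment level would remain at Day 28. This assumes simple decay and that capsule half-lives in healthy volunteers carry over to these patients. How many grades would be missed cannot be derived.

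The period is undefined for early stoppers. Selective loss of post-stop peaks is a possibility that the wording allows, not something the SAP prescribes. Nor should the point be read as saying that Day 28 values go unanalysed or that liver toxicity after treatment would be hidden. The gap matters most for haemoglobin and lymphocytes, which have stopping rules in Protocol 6.1.2 but no category table of their own.

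**What to change.** In SAP 4.10.4, define the table as each subject's worst post-baseline CTCAE grade over all scheduled and unscheduled values from first dose through Day 28, for all treated subjects regardless of when dosing ended. A window to 30 days after the last dose, matching SAP 4.10.1, would also serve. State the same window for Table 1 in SAP 4.10.4.1, which now has none. The on-treatment table can stay alongside, with treatment period defined for subjects who stop early.

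The cost is a sentence or two in the SAP and one more table run. No new data are needed. The downside is that values after Day 14 are sparse and the unscheduled ones will come mainly from sicker subjects. Showing the number of subjects per arm with any value after Day 14 would let readers judge this.
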